4.1. Number of volunteers::45

4.2. STATISTICS

In the analysis of the results to be obtained in our study, SPS statistics 22.0 version of SPSS statistics will be used under the Windows operating system Statistical Package for Social Sciences (SPSS). Descriptive statistical information shall be shown as arithmetic mean \pm Standard Deviation (\bar{x} istatistiksel \pm Ss) or percentage (%) and the statistical significance level shall be considered as $p \leq 0.05$.

The difference between the groups will be tested by two-factor variance analysis.

The two-factor variance analysis for correlated or repetitive measurements is an independent variable with two or more groups and associated or repeated measurements. Associated or repetitive measurements should be performed on the same subjects at specific time intervals. The purpose of this test is to determine the effect of the independent variable on the associated measurements. Specifically, it is to determine whether the groups of the independent variable have a different effect between the associated or repeated measures. TWO-WAY ANOVA

5. Center / centers where the research will be carried out: The research will be conducted between December 2018 and December 2019 in "Gerçek Dünya" special education and rehabilitation center and "Fark" special education and rehabilitation center.

6. Applicant's:

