4. MATERIÉLS AND METHOTS

Mental disability levels IQ = 50-79 individuals with mild / border mental disabilities will be included in the study. The disability status of the individuals will be determined by the health report, and the cognitive status of the individuals will be determined by the report given as a result of the evaluation made by the Guidance Research Centers of the National Education Directorates. The 45-person study group will be randomized to 3 groups of 15 persons each. The first group will not be subjected to any application except education. The second group will be the control group and will be taken to the balance training in addition to normal education. In the third group, dual task balance training will be applied within the scope of cognitive rehabilitation. The study will be held from December 2018 to December 2019. Intelligence-related parts of the assessments will be carried out by the expert psychologist. The studies were planned to be 2 times a week for 12 weeks. Before the beginning of the study, at the end and 3 months after the end of the study, the assessments for the groups will be applied and the results will be evaluated statistically within and between the groups. Inclusion

criteria; IQ 50-79, 6-13 years old, take command of Turkish, do not have physical disability, not have metabolic and systemic disease. To have a report on the mental disability and education required by the Ministry of National Education.

Exclusion criteria; To have any situation that prevents the taking of commands related to the exercise program to be implemented, To have a chronic systemic disease, To have an educational diagnosis other than the mental disability.

MOXO Attention Test: Attention, Timing, Impulsivity and Hyperactivity were found to be very effective in measuring performance levels; however, the rapidly increasing popularity of the test is due to the unique Distractor System found in MOXO.

To be able to focus on a simple MOXO task, the individual must ignore the visual and auditory distractors in the test, just as they should do in the same daily life. Individual; In order to achieve this, they must ensure the active inhibition of distractors, which makes the test even more challenging and the advanced characteristics of the test.

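### The between-group test treats the pre-training score as one level of the outcome instead of as a covariate, which gives up some precision with 15 children per arm

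*Protocol*

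**What the plan says.** Section 4.2 names the between-group test outright: "The difference between the groups will be tested by two-factor variance analysis". It then says which two-factor analysis is meant: "The two-factor variance analysis for correlated or repetitive measurements is an independent variable with two or more groups and associated or repeated measurements". The purpose follows: "Specifically, it is to determine whether the groups of the independent variable have a different effect between the associated or repeated measures". In usual terms this is a mixed repeated-measures ANOVA with the group-by-time interaction as the term of interest. Significance is set at p ≤ 0.05.

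Section 4 supplies the design. On allocation: "The 45-person study group will be randomized to 3 groups of 15 persons each". Assessments take place "Before the beginning of the study, at the end and 3 months after the end of the study", and the results are to be evaluated both within and between groups. The protocol mentions no covariate and no baseline adjustment.

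That the pre-training score is a level of the time factor is an inference from these two sections together. It is the plain reading, and nothing in the document contradicts it.

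**The concern.** In a randomised trial the pre-training score cannot carry a treatment effect. Any group difference there is chance, and the score is most useful as a predictor of the later score. When it enters as a level of the outcome, each baseline-to-visit comparison inside the interaction subtracts the whole baseline value instead of regressing on it. Unless the pre/post correlation is close to 1, that over-corrects and adds noise to the group contrast.

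What is at stake is precision. With 15 children per arm there is little to spare, and the pre-training value of each outcome is already being collected. The protocol names and explains this test, so the point concerns a stated choice and not a detail left for a later analysis plan.

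**Working it through.** **Inputs from the protocol.** 45 children, 3 groups of 15 (3 × 15 = 45, which agrees); three assessments; significance level 0.05. The protocol gives no power, effect size, SD, pre/post correlation or dropout figure, so there is no planned figure to reproduce.

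**Assumptions.** Unit SD at each visit; equal correlation rho between visits (compound symmetry) unless stated; effects of 0, 0.4 and 0.8 SD in groups 1, 2 and 3; no missing data; rho from 0.3 to 0.9.

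**Step 1: variance at one visit.** The group contrast in change from baseline has variance proportional to 2(1 − rho). The baseline-adjusted contrast has variance proportional to 1 − rho². The ratio is (1 − rho²) / [2(1 − rho)] = (1 + rho)/2, which is below 1 for every rho below 1. Estimating the slope from 45 children multiplies this by about 1 + 1/40 = 1.025. The net ratio stays below 1 while rho is below 2/1.025 − 1 = 0.95. Dividing 15 by the net ratio gives the equivalent number per arm.

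**Step 2: power at the same visit.** Simulation with 40,000 runs per scenario (Monte Carlo standard error at most 0.25 points) compared change-score ANOVA, F(2,42), with ANCOVA, F(2,41), both at 0.05. This comparison isolates the covariate's own contribution.

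| rho | (1+rho)/2 | with small-sample cost | equivalent per arm | power, change score | power, ANCOVA |
|---|---|---|---|---|---|
| 0.3 | 0.65 | 0.67 | 22.5 | 34% | 48% |
| 0.5 | 0.75 | 0.77 | 19.5 | 46% | 57% |
| 0.7 | 0.85 | 0.87 | 17.2 | 68% | 75% |
| 0.8 | 0.90 | 0.92 | 16.3 | 86% | 89% |
| 0.9 | 0.95 | 0.97 | 15.4 | 99% | 99% |

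The mean 95% confidence half-width for group 3 minus group 1, change score against ANCOVA, is 0.73 against 0.64 SD at rho 0.5, 0.57 against 0.53 at 0.7, and 0.46 against 0.45 at 0.8.

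**Step 3: the planned test against the proposed one.** The interaction has (3 − 1)(3 − 1) = 4 and (45 − 3) × 2 = 84 degrees of freedom. It is set against ANCOVA at both later visits, each at 0.025, counting at least one significant result. The first three rows have the 0/0.4/0.8 SD effects at end of training. In the last row half of that effect is present at end of training and all of it at 3 months.

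| Effect pattern | rho 0.5 | rho 0.7 | rho 0.8 |
|---|---|---|---|
| half retained at 3 months | 36% vs 49% | 58% vs 67% | 78% vs 83% |
| fully retained | 47% vs 65% | 72% vs 81% | 90% vs 93% |
| grows to 1.5 times | 74% vs 89% | 94% vs 97% | 99% vs over 99% |
| delayed | 36% vs 49% | 58% vs 67% | 78% vs 83% |

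Part of this gain comes from testing the visits separately with 2-df tests. Only step 2 measures the effect of the covariate alone.

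**Step 4: false positives per outcome.** With no effect and rho from 0.3 to 0.9, the interaction rejects in 4.9 to 5.1% of runs. Two ANCOVAs at 0.025 each reject at least once in about 4.5 to 5.1%, and at 0.05 each in 9.1 to 9.7%. If the correlation between the pre-training and 3-month scores is 0.2 lower than the other two, so that sphericity fails, the uncorrected interaction rejects in about 5.2 to 6.2% (rho 0.5 to 0.8). A Greenhouse-Geisser correction brings it back to about 4.8 to 4.9%.

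**The case against.** The strongest reply is that a group-by-time ANOVA on randomised groups is a legitimate test of the question section 4.2 asks. It also serves the within-group evaluation promised in section 4, which ANCOVA does not. On this view the point is one statistician's preference between two acceptable tests. The first part stands: the planned test is not an error, and the ANOVA should be kept for the within-group changes. The charge of preference does not quite stand, because the protocol fixes the between-group method and a more precise one is available from data already collected.

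The second reply is that the size depends on a correlation the protocol does not give. This stands. Ages run from 6 to 13 and several outcomes look like raw scores, which could push rho up; the IQ band of 50 to 79 could push it down for the intelligence test. Neither can be settled from the document.

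A third reply is that ANCOVA at end of training alone could do worse than the plan. This also stands. With the delayed effect above, it has about 18%, 24% and 32% power at rho 0.5, 0.7 and 0.8, against 36%, 58% and 78% for the interaction. The protocol ranks neither later visit above the other, so the remedy should not do so by default.

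Two stronger readings are tempting. A reader might infer that using the baseline as an outcome level biases the comparison or makes the test invalid. Randomisation and the error rates in step 4 do not support that, beyond a slight excess when sphericity fails and no correction is used. A reader might also take the first sentence of section 4.2 to mean the group main effect, which the pre-training score dilutes (simulated power of 24 to 38% with the effect fully retained). The sentence on purpose, "Specifically, it is to determine whether the groups of the independent variable have a different effect between the associated or repeated measures", points to the interaction, so that larger loss should not be attributed to the plan.

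**Conclusion.** The point holds as a minor loss of efficiency. At a given visit the stated approach uses a contrast with more variance than necessary by a factor of 2/(1+rho), before the small cost of estimating the slope. After that cost, adjustment is worth about 4.5 extra children per arm at rho 0.5, about 2 at 0.7, about 1 at 0.8 and next to nothing at 0.9.

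The variance ratio needs only equal SDs at the two visits and a linear relation between the scores. The power figures also rest on the assumed effects, normal data and complete follow-up. Since the protocol supplies no rho or effect size, the gain is modest and uncertain. In every scenario run, ANCOVA at 0.025 per visit was at least as powerful as the interaction and kept the overall level per outcome at about 5%.

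**What to change.** Replace the sentence naming the between-group test with wording such as: *For each outcome, the groups will be compared at end of training and at 3 months by analysis of covariance, with group as factor and the pre-training value of that outcome as covariate. Each visit is tested at 0.025, and adjusted differences are reported with confidence intervals. Pairwise comparisons at a visit are made only after a significant overall group test at that visit. The two-factor ANOVA, with Greenhouse-Geisser correction, is supportive and describes within-group changes.*

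A single main visit should be named only if the sponsor has a prior reason to rank the visits.

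Cost: no new data are needed, and SPSS 22, already named in section 4.2, fits these models. Each model spends one degree of freedom on the covariate. The significance level is divided over two visits; without that division the false-positive rate per outcome would be 9.1 to 9.7%. The split covers the two visits within one outcome and does not address the number of outcomes.

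### The only between-group test is a three-visit repeated-measures ANOVA, which in its classical form discards the baseline and end-of-training scores of any child who misses only the 3-month visit

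*Protocol*

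**What the plan says.** All in the Protocol:

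- **Design (Section 4).** "The 45-person study group will be randomized to 3 groups of 15 persons each". Assessments take place "Before the beginning of the study, at the end and 3 months after the end of the study", and "the results will be evaluated statistically within and between the groups".
- **Between-group test (Section 4.2).** "The difference between the groups will be tested by two-factor variance analysis". No other inferential method is named.
- **Form of that test (Section 4.2).** "The two-factor variance analysis for correlated or repetitive measurements is an independent variable with two or more groups and associated or repeated measurements". It adds: "Associated or repetitive measurements should be performed on the same subjects at specific time intervals". The stated aim is to learn "whether the groups of the independent variable have a different effect between the associated or repeated measures", which is the group-by-visit interaction. The paragraph ends by labelling the method a two-way ANOVA.
- **Software (Section 4.2).** "SPS statistics 22.0 version of SPSS statistics will be used". The SPSS procedure is not named.

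That all three visits enter one ANOVA is the natural reading of Sections 4 and 4.2 together, though it is not stated word for word.

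**The concern.** The classical group-by-visit ANOVA needs a full row of scores for every child. With three visits, one missing 3-month score removes the child from the analysis of that outcome, including baseline and end-of-training scores that were collected.

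Two things are at stake:

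- **Precision.** The comparison of change over the 12 weeks of training loses children because of a later visit that it does not use. With 15 per arm, each deleted child is 1/15 = 7% of the arm.
- **Who is compared.** The analysed children are no longer all those randomised. If loss differs between arms and is related to how the child scored at 12 weeks, the contrast shifts, in a direction that depends on which arm loses children.

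The objection is to the method the Protocol fixes, not to the absence of a missing-data rule.

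**Working it through.** **Inputs from the Protocol:** 3 arms × 15 = 45 children; three visits; significance level 0.05. The total of 45 cannot be reproduced as a powered sample size, because no effect size, SD, power or dropout rate is given.

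**Assumed inputs:** loss at the 3-month visit only; score SD of 1 at each visit; baseline-to-12-week correlation r of 0.5 or 0.7; true difference of 0.8 SD in baseline-to-12-week change.

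**1. Rows and scores lost.** If a fraction d miss only the last visit, complete children = 45(1 − d) and observed scores discarded = 2 × 45 × d per outcome.

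| d | complete children | observed scores discarded |
|---|---|---|
| 5% | 42.75 | 4.5 |
| 10% | 40.5 | 9 |
| 20% | 36 | 18 |
| 30% | 31.5 | 27 |

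**2. Precision of the 12-week change contrast.** SD of change = √(2(1 − r)), which is 0.775 at r = 0.7 and 1.0 at r = 0.5. The standard error of a pairwise difference is SD × √(2/n), and the 95% half-width multiplies this by t on 2n − 2 degrees of freedom. At r = 0.7:

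- n = 15: 2.048 × 0.775 × √(2/15) = 0.58 SD
- n = 12: 2.074 × 0.775 × √(2/12) = 0.66 SD

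Power is two-sided at 0.05 from the noncentral t, with noncentrality 0.8 divided by the standard error (2.83 at n = 15 and 2.53 at n = 12 for r = 0.7).

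| n per arm | power, r = 0.7 | half-width, r = 0.7 | power, r = 0.5 | half-width, r = 0.5 |
|---|---|---|---|---|
| 15 (all observed) | 0.779 | 0.579 | 0.562 | 0.748 |
| 14 (one lost per arm) | 0.749 | 0.602 | 0.531 | 0.777 |
| 12 (20% lost) | 0.677 | 0.656 | 0.466 | 0.847 |

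A simulation with 15 per arm, r = 0.7 and 20% random loss gave an SD of the contrast of 0.319 with complete rows and 0.282 with all observed rows.

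**3. The interaction test that Section 4.2 names.** Take assumed gains of 0, 0.25 and 0.5 SD in the three arms, equal at both later visits, and compound symmetry. The squared interaction terms sum to 1/12, so the noncentrality is n/(12(1 − r)), with 4 and 2(N − 3) degrees of freedom. Going from 15 to 12 complete children per arm, power falls from 20% to 16% (r = 0.5), 32% to 25% (r = 0.7) or 46% to 37% (r = 0.8). These are losses against full data. A mixed model recovers only part of them, because the missing 3-month scores stay missing.

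**4. Shift of the contrast.** If loss depends on the 12-week score, the shift in mean change is (1 − r) times the shift in the mean 12-week score of the children retained. With 20% loss in one arm:

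| loss mechanism | r = 0.7 | r = 0.5 |
|---|---|---|
| logistic slope 0.7 | 0.040 SD | 0.065 SD |
| logistic slope 1.5 | 0.068 SD | 0.113 SD |
| exactly the lowest 20% lost (bound) | 0.105 SD | 0.175 SD |

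In a harsher scenario, loss in one arm depends on the gain itself (slope 1.5, r = 0.7). A true contrast of 0.50 SD then averages 0.61, 0.68 or 0.75 SD in complete cases at nominal loss of 10%, 20% or 30%. It averages 0.50 SD when all observed end-of-training scores are used.

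**5. Does the alternative recover the scores?** A maximum-likelihood fit of the three-visit model with unstructured covariance, to 45 simulated children with 9 missing 3-month scores, returned each arm's 12-week change exactly equal to the mean over all 15 children. Complete rows gave different values. With score-dependent loss in one arm, the all-rows shift was 0.00.

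**The case against.** The strongest reply is that this is a missing-data point in another form. With complete data the named ANOVA discards nothing, and an unseen SAP might impute the 3-month scores or add a separate end-of-training analysis. For loss at 3 months only, a two-visit ANOVA would give the same 12-week point estimate as the mixed model. The SPSS procedure is unnamed, attrition, effect and correlation are all assumed, and the power figures in step 2 are for a pairwise contrast that Section 4.2 does not name. A group-by-visit ANOVA is also a conventional and valid test of the stated question.

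Much of this stands as a limit on size. With no missed visits there is no cost, one child lost per arm costs about 3 points of power, and the interaction test in step 3 has low power under its assumed effects even with no loss.

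It does not remove the point. The Protocol itself fixes the method. An SAP that kept the ANOVA unaided would keep the deletion, and one that replaced it would depart from Section 4.2. A two-visit ANOVA would be a further analysis that Section 4.2 does not name, and it would leave the three-visit test still dropping those children.

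**Conclusion.** The concern holds. The Protocol's only between-group test, read as the classical ANOVA it describes, throws away observed baseline and end-of-training scores whenever a child misses only the 3-month visit. Precision is the main cost: at an assumed 20% loss, roughly 10 points of pairwise power for 12-week change and a confidence interval about 12% to 13% wider (0.656/0.579 and 0.847/0.748 − 1). The shift is small if loss follows the 12-week score, and reaches 0.11 to 0.25 SD only in the scenario where loss in one arm follows the gain.

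This rests on three things: the classical form is run, all three visits enter one analysis, and some children miss the last visit. The Protocol supports the first two by its wording and gives no figure for the third. This does not make the test invalid, but the method is inefficient and is cheap to improve in a trial with 15 children per arm.

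**What to change.** In Section 4.2, replace the sentence naming the ANOVA, and the description that follows it, with:

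> Each outcome will be analysed with a linear mixed model (SPSS MIXED, long format) on all three visits, with group, visit and group-by-visit as fixed effects, unstructured covariance across visits and Satterthwaite degrees of freedom. All randomised children with any available score are analysed in the group assigned. Between-group differences in change from baseline at the end of training and at 3 months, and the within-group changes, are contrasts from this model.

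This tests the same group-by-visit effect and supplies the within- and between-group results that Section 4 promises. It needs no new data, visits or software. The cost is some extra analysis work (long-format data, contrasts written out) and the need for small-sample degrees of freedom. The model still assumes that a missed visit depends only on scores already observed.
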